8.1.3.2 Baseline Functional and Behavioral Assessments

Participants will receive a unique URL link by e-mail to complete the following functional and behavioral assessments electronically through the LORIS survey tool. Site study staff may also be available by phone/video-call to assist participants in completion of these questionnaires if preferred. Paper versions of the questionnaires may also be sent to participants by mail to complete at home and return to the site if preferred or requested by the participant. (Total estimated time: 30 minutes):

- Geriatric Depression Scale (GDS)
- Generalized Anxiety Disorder 7-Item Scale (GAD-7)
- Sleep Disorders Questionnaire
- COVID-19 Impact Survey
- Research Satisfaction Survey

The following questionnaire will be completed by study partner (if available).

- Mild Behavioral Impairment Checklist (MBI-C) (estimated time: 10-15 minutes)

8.1.4 ***Additional Remote Baseline Testing***

Following completion of the baseline procedures above, participants will also complete the following assessments remotely within approximately 2 weeks:

- BHPro registration and completion of lifestyle risk questionnaires and goal setting (estimated time to complete is 1.0 hour; see section [8.3](#))
- Weekly participation in BHPro (approximately 40 minutes/week)
- “Burst” Cognitive Testing (5-10 minutes/day for 6 consecutive days following initial testing at Baseline Visit)
- Cogniciti Brain Health Assessment (estimated time to complete is 20 minutes)
- Actigraphy recording (continuous recording for 14 consecutive days)
- EEG recording (nightly recordings for 3 consecutive nights)

8.1.5 ***Month 3 Remote Follow-Up and Testing***

Participants will receive a follow-up phone call from a site study team member at approximately month 3 following baseline to assess continued interest in BHPro participation and satisfaction with BHPro.

Participants will also receive notifications to complete the following activities remotely at month 3:

- Notification via the MyCogHealth app will be sent to participant to complete “Burst” Cognitive Testing (estimated time: 5-10 minutes/day for 7 consecutive days)
- Lifestyle risk questionnaires and goal setting within BHPro (estimated time: 20-30 minutes; see section [8.3](#))

8.1.6 **Month 6 Remote Follow-Up and Testing**

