Participants will receive a follow-up phone call from a site study team member at approximately month 6 following baseline to assess continued interest in BHPro participation, and review any medical, lifestyle and diagnostic changes that have occurred since the baseline visit. The phone call will take an estimated 0.5-1.0 hours to complete.

Participants will also complete the following cognitive assessments remotely:

- Notification via the MyCogHealth app will be sent to participant to complete “Burst” Cognitive Testing (estimated time: 5-10 minutes/day for 7 consecutive days)
- Study coordinator will send participant an email that contains a personalized link to complete the Cogniciti Brain Health Assessment (estimated time: 20 minutes)
- BHPro outcome assessments (program usability and acceptability, dementia literacy, self-efficacy, attitudes toward dementia; see section [8.3](#)). These will be completed online within BHPro (estimated time: 30-45 minutes)
- Lifestyle risk questionnaires and goal setting within BHPro (estimated time: 20-30 minutes)

8.1.7 **Month 9 Remote Follow-Up and Testing**

Participants will receive a follow-up phone call from a site study team member at approximately month 9 following baseline to assess continued interest in participation and satisfaction with BHPro.

Participants will also receive notifications to complete the following activities remotely at month 9:

- Notification via the MyCogHealth app will be sent to participant to complete “Burst” Cognitive Testing (estimated time: 5-10 minutes/day for 7 consecutive days)
- Lifestyle risk questionnaires and goal setting within BHPro (estimated time: 20-30 minutes)

8.1.8 **Month 12 Remote Visit**

Participants will complete the following procedures remotely via video-conference with a member of the study team at approximately Month 12 for a remote re-assessment.

Study participants will undergo the following procedures (Estimated Time to Complete: 4.0-5.0 hours):

- Documentation of changes to medical history (including medication changes and any medical procedures) that have occurred since the time of the last assessment
- Self-report weight
- Body Mass Index (BMI) calculation (based on self-report current height and weight)
- Brief Remote Neurological Exam (completed by Site Principal Investigator or qualified medical professional)
- Lawton Brody IADL
- MoCA

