MyCogHealth is an iOS/Android app for self-administered cognitive assessments and customizable surveys of health behaviors, risk factors, and patient-reported outcomes. The MyCogHealth app currently supports iPhones from version 6 and up (running iOS 11 and up). The app also supports Android 6 and up. The software is built on Health Insurance Portability & Accountability Act (HIPAA)-compliant scheduling and data management server-side software that permits individually tailored assessment protocols and scheduling. The platform is user-friendly and was developed for use with older adults. Based on available data pertaining to smartphone use and ownership in this age population, we anticipate that the majority of participants will have a personal smartphone that is compliant with this program. With assistance from a study team member, each participant will install the mobile application software on their personal mobile device. For individuals lacking a compliant smartphone, CTU will provide up to 150 participants with Android devices, including training. Participants will be oriented to the application software during the baseline remote video-conference, and will complete a training session on the mobile battery with the study team member present via video-conference to answer questions and trouble-shoot any issues that may arise. Ongoing technical support may also be provided to participants, over the duration of their participation in the 12-month BHSP, as needed through [name] CogTech Group at the University of Victoria. For the purposes of providing technical support, participant contact information (name, telephone number, email address) and study ID may be sent by encrypted email to study staff at the CogTech Group at the University of Victoria.

“Burst” cognitive testing using the MyCogHealth app will consist of five measurement “bursts” over approximately 12 months, at Baseline, Month 3, 6, 9 and 12. Each measurement burst will involve two mobile assessment sessions per day for seven consecutive days, with sessions that take approximately 5-10 minutes to complete. Each session includes 3 cognitive tests, Symbol Match, Dot Memory, and Trail-Making A and B, as well as several brief questions assessing state factors at the time of testing (e.g., mood, fatigue, subjective impression of cognitive ability). See section [10.1.6](#) for full description of cognitive measures.

9.3 ***Physical Activity and Sleep Monitoring***

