¹Procedures and assessments completed by telephone or video-conference between participant, study partner (if applicable) and study site team member.²Height will not be collected at Month 12.

³ If no study partner/informant available the Global CDR score will be determined by research team consensus using all other available information and best clinical judgement.

⁴To be completed by site Principal Investigator or other medically qualified professional following the recommended Telemedicine guidelines for neurological exams provided by AAN.

⁵Medical and diagnostic changes only to be completed at Month 6 follow-up phone call.

⁶Neuropsychological Test Battery to be completed by video-conference between participant and trained rater. Instructions and administration adapted for remote use and provided in Study Procedures Manual.

⁷Instructions and initial testing for “Burst” Cognitive Testing will be completed during remote baseline video-conference. Participants will receive notification by smartphone (for “burst” cognitive testing) and by email to complete other timepoints remotely. The Neuropsychological Test Battery should be completed prior to the start of “Burst” Cognitive Testing at Baseline and Month 12.

⁸Participants will receive a personalized link sent by the study coordinator to complete the Cogniciti BHA. “Burst” Cognitive Testing should be completed prior to the Cogniciti BHA at Baseline, Month 6 and Month 12.

⁹Participants will receive a personalized link sent through the LORIS survey tool to complete the behavioral and functional self-report measures.

¹⁰The MBI-C will be completed by Study Partner/Informant if available.

¹¹Devices and user instructions will be sent to participants from SRI by mail. Application and Instructions on use and duration of Axivity device, and EEG headband will be provided by video-conference between participant and SRI study team member. At the conclusion of the specified recording period, devices will be returned by mail. The same procedure will be followed for Month 12.

¹²A saliva sample with at-home collection kit will be provided for genomics testing (PHS) and analysis.

¹³These assessments will be completed online through the BHPro website.

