8.4.4 Cognition

8.4.4.1 Change in **global cognition** will be assessed using a composite outcome score computed from the following measures from Neuropsychological Test Battery:

- Craft Story – Immediate Recall – Total Story Units Recalled - Verbatim
- Craft Story – Delayed Recall – Total Story Units Recalled - Verbatim
- ADAS-COG Word Recall – Total Immediate Recall (trial 1 + trial 2 + trial 3)
- ADAS-COG Word Recall – Delay (total correct)
- Brief Visuospatial Memory Test-Revised (BVMT-R)- Total Recall (trial 1 + trial 2 + trial 3)
- BVMT-R Delayed Recall
- Oral Symbol Digit Modalities Test – Total Raw Score
- Oral Trail Making Test (Part A) – Time To Completion
- Oral Trail Making Test (Part B-A)
- DKEFS Category Fluency – Total Correct (animals only)
- DKEFS Color-Word Interference Test (CWIT) – Condition 2 Word Reading – Time to Complete

- DKEFS CWIT – (Condition 3 Inhibition-Condition 2 Word Reading)

Z-scores for each participant on each measure will be calculated using the overall mean and SD of all participants at baseline as reference. Scores from each individual test will be converted to z-scores that typically range from -3 to 3, with higher scores reflecting better performance, and averaged to form a composite. For purposes of this analysis, the z scores for the timed tasks (Oral Trail Making Test (Part A and Part B) and Color-Word Interference Test (Word Reading and Inhibition)) are reverse coded. If more than 25% of the component measures are missing, the global cognitive composite score will be missing.

An MMRM will be used to evaluate change in the global cognitive outcome from baseline to Month 12, adjusted for baseline characteristics including age, sex, race, cognitive status and education. The MMRM will be fit to the ITT sample (that is, the same multiply imputed dataset described in section 8.1), to the mITT sample, and to the 'completers' sample. Inference on the change will be conducted through least-square means estimates.

Additional exploratory analysis will be conducted by analyzing the data obtained by first calculating the domain-specific outcomes (see section 8.4.4.2 below), and then aggregating the domain-specific outcomes to calculate the global cognitive outcome score. Methods similar to the above will be used for the analysis.

8.4.4.2 Change in the subdomains of memory, processing speed, and executive functions will be assessed using domain-specific composites.

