The memory subdomain is comprised of the following tests:

- Craft Story – Immediate Recall – Total Story Units Recalled - Verbatim
- Craft Story – Delayed Recall – Total Story Units Recalled - Verbatim
- ADAS-COG Word Recall – Total Immediate Recall (trial 1 + trial 2 + trial 3)
- ADAS-COG Word Recall – Delay (total correct)
- BVMT-R Total Recall (trial 1 + trial 2 + trial 3)
- BVMT-R Delayed Recall

The processing speed subdomain is comprised of the following tests:

- Oral SDMT – Total Raw Score
- Oral TMT (Part A) – Time To Completion
- DKEFS CWIT – Condition 1 Color Naming – Time to Complete

The Executive Functions subdomain is comprised of the following tests:

- Oral Trail Making Test (Part B – Part A)
- DKEFS Category Fluency – Total Correct (animals only)
- DKEFS CWIT- (Condition 3 Inhibition- Condition 2 Word Reading)

Z-scores for each participant on each measure will be calculated using the overall mean and SD of all participants at baseline as reference.

To calculate each domain-specific cognitive composite, scores from each individual test within the subdomain will be converted to z-scores that typically

range from -3 to 3, with higher scores reflecting better performance, and averaged to form a composite. For purposes of this analysis, the z scores for the timed tasks (Oral Trail Making Test (Part A and Part B) and Color-Word Interference Test (Word Reading and Inhibition)) are reverse coded. Composite scores are computed when 50% or more of the component test scores are available.

An MMRM will be used to evaluate change from baseline to Month 12 in each of the domain-specific composites z-scores, adjusted for baseline characteristics including age, sex, race, cognitive status and education. The MMRM will be fit to the ITT sample (that is, the same multiply imputed dataset described in section 8.1), to the mITT sample, and to the 'completers' sample. The change will be estimated using the least-square mean contrast.

8.4.4.3 Change in performance based on “**Burst**” Cognitive Testing (**MyCogHealth Mobile App**) that addresses: 1) Within-person change in asymptote, daily variation and within-burst practice effects of “burst” cognitive testing; 2) Between- and within-person factors including self-rated emotional reactivity and its association with variation in cognitive performance over the BHPro intervention

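### Up to 56 burst sessions of related tasks fall between the baseline and Month 12 neuropsychological batteries, and the SAP cannot show whether a gain, above all in processing speed, depends on that practice

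*SAP*

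**What the plan says.** **Burst schedule.** Protocol 9.2.2 places bursts "at Baseline, Month 3, 6, 9 and 12". It adds: "Each measurement burst will involve two mobile assessment sessions per day for seven consecutive days". On content: "Each session includes 3 cognitive tests, Symbol Match, Dot Memory, and Trail-Making A and B". Protocol 10.1.6 repeats the two-a-day schedule and gives Symbol Match 12 trials per session.

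**Order.** Protocol Appendix 2, footnote 7: "The Neuropsychological Test Battery should be completed prior to the start of" burst testing at Baseline and Month 12.

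**Conflicting dose.** Protocol 8.1.4 describes the baseline burst as "5-10 minutes/day for 6 consecutive days following initial testing at Baseline Visit". Sections 8.1.5 to 8.1.7 and 8.1.8.2 describe the later bursts as "5-10 minutes/day for 7 consecutive days". Sections 9.2.2 and 10.1.6 give 5-10 minutes as the length of one session, with two sessions a day.

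**Composites.** SAP 8.4.4.1 lists 12 global components, among them Oral SDMT, Oral TMT A and Oral TMT B-A. In SAP 8.4.4.2, "The processing speed subdomain is comprised of the following tests" introduces three tests: Oral SDMT, Oral TMT A and CWIT Color Naming. The executive composite is Oral TMT B-A, animal fluency and CWIT inhibition minus word reading.

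**Model.** "An MMRM will be used to evaluate change in the global cognitive outcome from baseline to Month 12", with adjustment for age, sex, race, cognitive status and education. The subdomains are handled the same way. Practice and retest effects are modelled only for the burst data (SAP 8.4.4.3), where the planned link to the NTB is concordance.

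**The concern.** The baseline NTB precedes all burst testing. The Month 12 NTB comes after four bursts that exercise symbol matching and trail making. If that practice carries over at all, it would tend to raise Oral SDMT and Oral TMT A scores. The Month 12 contrast then mixes the study's own testing with any change following BHPro. There is no comparison group to subtract it, no exposure term in the model, and no alternate NTB form mentioned in either document.

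Aim B.iii is change in cognition following participation. Practice could produce an apparent gain or mask a decline. Protocol 1.2 hopes to identify people on a declining trajectory for later trials, and Protocol 8.2 uses the study data to model the platform trial, so the reading of these composites matters beyond one exploratory table.

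**Working it through.** **1. The plan's own figure.** Protocol 13.1 expects about half of 350 participants to own a suitable phone and supplies 150 more: 0.5 × 350 + 150 = 325. This reproduces. About 25 of 350 would have no device.

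**2. Scheduled exposure between the two NTBs** (Baseline, Month 3, 6 and 9 bursts)

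| Reading | Arithmetic | Sessions |
|---|---|---|
| Sections 9.2.2 and 10.1.6 | 4 × 7 × 2 | 56 |
| Baseline burst as one training session plus 6 days | 1 + 6 × 2 + 3 × 14 | 55 |
| Visit schedule read as one session a day | 4 × 7 | 28 |

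These are scheduled maxima for people with a device, not completed sessions.

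**3. How alike the tasks are**

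| NTB test | Burst counterpart | Difference |
|---|---|---|
| Oral SDMT: spoken symbol-to-number coding, 120 s (10.1.4.5) | Symbol Match: on-screen choice between symbol pairs (10.1.6) | Stimulus and response mode |
| Oral TMT A: counting aloud 1 to 25 (10.1.4.8) | Digital trail making (10.1.6) | Oral form removes visual and motor demands |
| Oral TMT B-A | Digital trail making | Difference score: equal shortening of A and B leaves it unchanged, and shortening A alone worsens it |

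The tasks are related. Oral SDMT is the most plausible route for transfer, and the sign for B-A is not fixed.

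**4. Shares.** Global 3/12, processing speed 2/3, executive 1/3.

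**5. Illustration.** Assumptions not in the documents: transfer g = 0.2 baseline SD per affected component, pre-post correlation r = 0.8, composite SD 1, no true change. From Protocol 13.1: n = 245 to 280 completers, two-sided 5%.

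- Shift = g × (affected components / all components).
- SE = √(2(1 − r)/n) = √(0.4/245) = 0.0404, or √(0.4/280) = 0.0378.
- P(significant) = Φ(shift/SE − 1.96) + Φ(−shift/SE − 1.96).

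| Composite | Affected | Shift | Shift/SE | P(significant) |
|---|---|---|---|---|
| Processing speed | SDMT only | 0.2/3 = 0.067 | 1.65 to 1.76 | 38-42% |
| Processing speed | SDMT and TMT A | 0.4/3 = 0.133 | 3.30 to 3.53 | 91-94% |
| Global | SDMT only | 0.2/12 = 0.017 | 0.41 to 0.44 | 7% |
| Global | All three | 0.6/12 = 0.050 | 1.24 to 1.32 | 24-26% |

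The last row assumes that B-A improves, which step 3 leaves open. No executive figure is given, for the same reason.

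**6. Sensitivity to the assumptions.** An average of k imperfectly correlated z-scores has SD √((1 + (k − 1)ρ)/k), which is below 1. With inter-test correlation ρ = 0.3 to 0.5 and r = 0.6 to 0.8 (also assumed), the four rows become 30-68%, 82-100%, 7-11% and 22-60%. With g = 0.1 and both speed tests affected, the processing-speed figure is 30-68%.

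**The case against.** The strongest reply is that the documents give no evidence of transfer. The NTB versions are oral, and nothing shows that tracing trails on a phone speeds counting aloud. The outcome is exploratory, the single-group design is declared, and the SAP claims within-person change rather than a causal effect. The three subdomains are already reported separately. Most of this stands. It makes the size unknown and the consequence modest, but it does not supply the missing check.

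Three stronger readings are tempting, and the documents do not support them.

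- **That the tasks are near-identical, so the Month 12 change is practice.** The test descriptions in Protocol 10.1.4 and 10.1.6 differ in stimulus and response mode.
- **That the composites without these tests are free of practice.** Dot Memory (recall of grid locations) resembles BVMT-R, which supplies 2 of 6 memory components. The Cogniciti BHA at Baseline and Month 6 includes a Stroop task related to CWIT. Ordinary 12-month retest affects every component.
- **That modelling the number of burst sessions by time would isolate the effect.** Session count is post-baseline and self-selected, plausibly tied to motivation, BHPro engagement and decline. About 25 people without a device, or 17 to 20 after 20-30% dropout (25 × 0.7 = 17.5; 25 × 0.8 = 20), are too few and not comparable.

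**Conclusion.** The gap is real and limited. Four bursts of related practice lie between the two batteries, and SAP 8.4.4.1-8.4.4.2 contains nothing to show whether an apparent gain depends on it. The concern is firmest for Oral SDMT, and hence for processing speed. It is weaker for the global score and undetermined in direction for the executive composite.

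On an assumed 0.2 SD transfer, a false processing-speed gain would be declared about 40% to 90% of the time, and a global one about 7% to 25%, against a nominal 5%. These figures rest on transfer and correlations that the documents do not give. They show what could happen, not what will. The primary ADKS analysis is not touched. This is a cheap improvement to an exploratory analysis.

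**What to change.** In SAP 8.4.4.1-8.4.4.2:

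1. Keep the planned composites as the main NTB results.
2. Prespecify sensitivity versions: a global composite without Oral SDMT, Oral TMT A and Oral TMT B-A (12 − 3 = 9 components), and an executive composite without Oral TMT B-A (2 components). State how the existing missing-component rules carry over.
3. For processing speed, report the change in each component. CWIT Color Naming is the one without a burst counterpart.
4. State in advance that a gain which disappears in these versions is compatible with practice. Do not present the reduced composites as practice-free or as the lead result.
5. State that NTB change, including memory and CWIT, still contains retest effects and cannot be attributed to BHPro alone.
6. Report completed burst sessions descriptively only.

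In the protocol, reconcile the daily burst dose in 8.1.4-8.1.7 and 8.1.8.2 with 9.2.2 and 10.1.6, so that exposure can be described correctly.

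**Cost.** SAP wording and a few extra model runs on data already in the plan. The reduced composites are slightly noisier. By the SD formula in step 6 with ρ = 0.3 to 0.5, and with r unchanged, the SE rises by about 1-3% for the global score (SD 0.599 to 0.615, or 0.736 to 0.745) and 6-10% for the executive score (0.730 to 0.806, or 0.816 to 0.866).

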Tests that have been administered clinically in the past 12 months will not be repeated (unless there is a discrepancy between test versions). Consent forms for each site will include a statement asking participants to allow for their clinical results from tests overlapping with the CTU battery to be entered into the CTU case report form. If a patient was assessed using a different version of the same test used in the CTU neuropsychological battery, the test will be repeated using the version consistent with the study.

Domain	Test	Description	Time (Mins)
Memory & Orientation	Craft Story 21 Immediate and Delayed Recall	Story learning and Recall	10-15
	ADAS-Cog Immediate & Delayed Word Recall	Word List Learning and Recall	10-15
	ADAS-Cog Orientation	Orientation	2-3
	Brief Visuospatial Memory Test - Revised	Figure learning and Recall	10-15
Attention, Processing Speed	Digit Symbol Modalities Test- Oral Version	Attention and Processing speed	5
	Oral Trail Making Test (Part A)	Visual and Motor Processing Speed	2-3
	DKEFS Color-Word Interference Test- Color Naming & Word Reading	Attention and Processing Speed	5
Executive Function	DKEFS Verbal Fluency	Phonemic (letter) fluency, Semantic (category) fluency, Category Switching	2
	Oral Trail Making Test (Part B)	Switching attention	3-5
	DKEFS Color-Word Interference Test- Inhibition	Inhibition	5-10
Visuoperceptual & Construction	Brief Visuospatial Memory Test- Revised Copy	Visuoconstruction	3
Speech & Language	Boston Naming Test-15 Item	Confrontational Naming	5-10

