10.1.4.6 DKEFS Color-Word Interference Test (CWIT)

This timed task requires participants to (1) name a series of colors, (2) read a series of words and then (3) name the color of the ink of dissonant color words (i.e., must say “green” when the word red is written in green ink) [30]. The latter task is a measure of response inhibition as participants must inhibit an overlearned verbal response of reading the particular word (red) in favor of generating a conflicting response of naming the different ink color (green). For the fourth trial, participants must alternate between naming the ink color of dissonant color words and simply reading the word and ignoring the ink color (inhibition and switching). The score is total time it takes to complete each trial. The maximum time for the color naming and word reading trials is 90 seconds and the maximum time for the inhibition and inhibition switching trials is 180 seconds.

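### The reverse-coding list in SAP 8.4.4.2 leaves out CWIT Color Naming time, one of the three processing-speed components, so the composite as written mixes directions

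*SAP*

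**What the plan says.** SAP 8.4.4.2 defines the processing-speed subdomain from three tests: "Oral SDMT – Total Raw Score", Oral Trail Making Part A time, and the completion time of CWIT "Condition 1 Color Naming". Each is converted to a z-score against the baseline mean and SD, "with higher scores reflecting better performance, and averaged to form a composite". The next sentence names the z-scores whose sign is changed: the "timed tasks (Oral Trail Making Test (Part A and Part B) and Color-Word Interference Test (Word Reading and Inhibition)) are reverse coded". The availability rule follows: "Composite scores are computed when 50% or more of the component test scores are available".

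SAP 8.4.4.1, on the main global composite, carries the same sign-reversal sentence. There the simple-speed CWIT score is Word Reading, not Color Naming. That section also plans an additional exploratory analysis "aggregating the domain-specific outcomes to calculate the global cognitive outcome score".

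Protocol 10.1.4.6 fixes the direction of the raw CWIT score: "The score is total time it takes to complete each trial". The test table in Protocol 10.1.4 puts "Color-Word Interference Test- Color Naming & Word Reading" together under attention and processing speed.

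**The concern.** Color Naming is a component of the composite and is scored as time, so an untouched z-score is higher for worse performance. The list of scores to reverse names two Trail Making parts and two CWIT conditions, and Color Naming is not among them. The paragraph therefore states an aim (higher is better) and an itemised procedure that does not achieve it for one of three components.

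If the list is programmed as it stands, slower color naming raises the processing-speed score, and real improvement on that test cancels improvement on the other two. Nothing in the output would look broken: the values would still be z-scores in a plausible range. Change in processing speed is a named exploratory outcome, and the domain-aggregated global score would inherit the error.

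**Working it through.** **Direction of each processing-speed component**

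| Component (SAP 8.4.4.2) | Raw direction | On the reversal list? | Sign in the composite if the list is followed |
|---|---|---|---|
| Oral SDMT total raw score | higher is better | no, correctly | + |
| Oral Trail Making Part A time | lower is better | yes | + |
| CWIT Color Naming time | lower is better (Protocol 10.1.4.6) | no | − |

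In 8.4.4.1 the same list serves, because the timed components there are Trail Making A, Trail Making B minus A, Word Reading, and Inhibition minus Word Reading. In 8.4.4.2 Word Reading enters only as the term subtracted in the executive-function difference score, so the list names a condition that is not a stand-alone component and omits one that is.

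**Inputs for size.** The plan gives no figure to reproduce here, and no expected gains or inter-test correlations. The assumptions are a uniform gain d = 0.20 SD on all three tests, equal pairwise correlation rho, and equal weights.

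**Mean change**
- All signs aligned: (d + d + d)/3 = 0.200.
- List followed literally: (d + d − d)/3 = d/3 = 0.067. The ratio of one third needs no correlation assumption.
- If only Color Naming improves, by 0.30 SD: +0.10 aligned, −0.10 literal.

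**Two of three tests available** (permitted by the 50% rule)
- SDMT or Trail Making A missing: (d − d)/2 = 0.000.
- Color Naming missing: (d + d)/2 = 0.200.

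The same true gain is thus scored differently according to which test is missing.

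**Domain-aggregated global score**, three domains weighted equally: (0.200 + 0.200 + 0.067)/3 = 0.156, which is 22% below 0.200.

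**Agreement between the two versions of the composite**
- Var(aligned) = (3 + 6·rho)/9
- Var(literal) = (3 − 2·rho)/9
- Cov = (1 + 2·rho)/9
- Correlation = (1 + 2·rho)/√[(3 + 6·rho)(3 − 2·rho)]

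| rho between tests | Calculation | Correlation |
|---|---|---|
| 0.3 | 1.6/√(4.8 × 2.4) | 0.47 |
| 0.5 | 2.0/√(6.0 × 2.0) | 0.58 |
| 0.7 | 2.4/√(7.2 × 1.6) | 0.71 |

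**Test of within-person change.** What counts here is the correlation r between change scores. With equal change-score variances, the ratio of expected test statistics (literal to aligned) under a uniform gain is (1/3)·√[(3 + 6r)/(3 − 2r)], which is algebraically the same expression as above evaluated at r.

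| r between change scores | Ratio |
|---|---|
| 0 | 0.333 |
| 0.1 | (1/3)·√(3.6/2.8) = 0.378 |
| 0.3 | (1/3)·√(4.8/2.4) = 0.471 |

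**The case against.** The strongest reply is that the intended direction is already on the page. The paragraph says higher is better and refers to timed tasks, Color Naming is listed as a time to complete, and the SAP's Summary of Changes gives the same purpose for the reversal. The list is also plainly shorthand: it names Part B and Inhibition, whereas the components are the differences B minus A and Inhibition minus Word Reading. A programmer must already read it with the higher-is-better aim in mind, and that aim covers Color Naming.

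This stands as far as intent goes, and it makes it likely that the gap would be noticed. It does not remove the contradiction. The shorthand at least points to the right tests, whereas Color Naming is not mentioned at all in a list that picks out CWIT conditions by name.

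Three narrower points also stand:
- The test-statistic ratios assume equal change-score variances. The SAP standardises to the baseline SD, which does not guarantee this.
- The two-of-three results apply directly to participants with a missing test. In the ITT analysis they also depend on whether components or composites are imputed, which SAP 8.1 does not settle.
- The possibility that Word Reading was the intended component has only indirect support: 8.4.4.1 uses it and Protocol 10.1.4 groups the two conditions. The explicit condition number in 8.4.4.2 favours Color Naming.

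**Conclusion.** The concern holds. As written, the sign rule in SAP 8.4.4.2 gives one of three processing-speed components the wrong direction and conflicts with the stated meaning of the score. That much is certain from the text. The effect on results depends on whether the list is coded literally. If it is, a uniform gain shrinks to one third. The expected test statistic falls to roughly 33% to 47% of its correct value over assumed change-score correlations of 0 to 0.3, given equal change-score variances. The aggregated global score loses 22% under equal domain weights. The 0.20 SD gain and the correlations are illustrative.

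The outcomes defined from this composite are exploratory: processing speed itself and the domain-aggregated global score. Other exploratory analyses of cognition, such as concordance with the neuropsychological battery or the polygenic score analyses, would be touched only if they use the processing-speed score, which the SAP does not say. ADKS, GSE, the sample size, the main 12-measure global composite, and the memory and executive-function composites do not depend on it. This should be fixed before the composites are analysed, but it does not threaten the trial's main conclusions.

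**What to change.** Replace the itemised list with a rule: before averaging, multiply the z-score of every time-based component by −1. If examples are wanted, give them by section:
- In 8.4.4.2: Color Naming, Trail Making A, Trail Making B minus A, and Inhibition minus Word Reading.
- In 8.4.4.1: the same, with Word Reading in place of Color Naming.

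Then check that the scoring code follows the rule, for instance by confirming that each component z-score correlates in the expected direction with its raw score.

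If Word Reading was in fact the intended processing-speed component, correct the component list instead. Either way, record which of the two was wrong, and decide it without reference to results.

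The first route costs a wording change and a code check. The second changes the definition of an exploratory outcome and should be dated and documented as such.
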